9.2.4 Handling of missing data

Imputation of missing data post-baseline will be employed using last observation carried forward (LOCF) for the endpoints of the change from baseline to subsequent time points in eGFR, LVMI, LVEF, lyso-Gb3 and urine protein / creatinine ratio. No data imputation will be done for the categorical analyses of the BPI (short form).

Imputation of missing dates 9.2.5

Any date that is collected only as MONTH / YEAR, e.g., date of birth, the 15th of the month will be imputed.

If AE start date is partial, the following imputation will be done:

- If day is missing, impute 1st of the month
- If day and month are missing, impute 01 July. However, this should be checked not to be later than the AE stop date. If AE stop date is available, the 1st of the month of the AE stop month should be imputed,

If AE stop date is partial, the following imputation will be done:

- If day is missing, impute end of the month $(30^{\text{th}} \text{ or } 31^{\text{st}})$
- If day and month are missing, impute 31 Dec.

If AE stop date is missing (i.e., AE still ongoing), and AE start date has missing day and month, and imputed AE start date per above rules (01July) is after date of death (DTHDT) or end of study date (EOSDT) then "01Jan" will be imputed as AE start date.

If imputed stop date is after date of death (DTHDT) or end of study date (EOSDT), AE end date will be imputed as date of death (DTHDT) or end of study (EOSDT).

The same rules above (for AE date imputation) will be followed for prior / concomitant medications and medical history.

TAK675-3001	Page 27 of 27
Statistical Analysis Plan Amendment 1	1-Feb-2024

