# **Appendix 3.2 Collection of Adverse Events**

All AEs/SAEs are collected from the time the informed consent document is signed until the defined follow-up period stated in Section 8.1.4. This includes events occurring during the screening phase of the study, regardless of whether or not investigational product is administered.

All AEs/SAEs must be followed to closure (the subject's health has returned to his/her baseline status or all variables have returned to baseline), regardless of whether the subject is still participating in the study. Closure indicates that an outcome is reached, stabilization achieved (the investigator does not expect any further improvement or worsening of the event), or the event is otherwise explained.

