6.6 Safety Analysis

The primary analysis will be the incidence of serious TEAEs.

Serious adverse events will be coded using the most recent version of Medical Dictionary for Regulatory Activities (MedDRA) coding dictionary. Serious treatment-emergent adverse events (serious TEAEs) will be summarized for overall and by system organ class (SOC) and preferred term (PT). Analysis of AEs will be performed at both subject level and AE level.

Subjects will be counted once per SOC and once per PT. Multiple events of the same type will be combined for each subject and, when doing this, the worst drug relationship, severity or outcome for each event type will be presented for the analysis. When calculating event rates, the denominator will be the total population size, irrespective of dropouts over the course of follow-up.

TAK675-3001	Page 20 of 27
Statistical Analysis Plan Amendment 1	1-Feb-2024

All summaries of AE and antibody data will be split by age group (2 to <12, 12 to <18, <18, \geq 18 years at Informed Consent, Total).

The safety set will be used.

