6.6.1 Adverse Events

Secondary safety analysis

The secondary safety analyses will be based on the safety set.

Adverse events will be coded using the most recent version of Medical Dictionary for Regulatory Activities (MedDRA) coding dictionary. A treatment-emergent adverse event (TEAE) is defined as any event emerging or manifesting at or after the initiation of treatment with an investigational product or medicinal product or any existing event that worsens in either intensity or frequency following exposure to the investigational product or medicinal product until the end of the safety follow-up period (14 days (+7 days) after the last infusion). Treatment-emergent adverse events (TEAEs) will be summarized for overall and by SOC and PT. Analysis of AEs will be performed at both subject level and AE level. Similar displays will be provided for IRRs. An IRR will be defined as an AE that 1) begins either during or within 24 hours after the start of the infusion and 2) is judged as related to study drug. The AEs will be summarized by severity, seriousness, and relation to investigational product.

Subjects will be counted once per SOC and once per PT. Multiple events of the same type will be combined for each subject and, when doing this, the worst severity or outcome for each event type will be presented for the analysis. When calculating event rates, the denominator will be the total population size, irrespective of dropouts over the course of follow-up.

All-cause mortality will be listed by subject. Two listings will be created – one listing the cause of death. The other listing will show serious TEAEs leading to death.

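### Partial AE start dates are imputed without reference to first dose, so a new on-treatment AE dated only to the first-dose month can be classed as pre-treatment (minor)

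*SAP*

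**What the plan says.** SAP 9.2.5 (Imputation of missing dates) gives these rules for a partial AE start date:

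- Day missing: "If day is missing, impute 1st of the month".
- Day and month missing: "If day and month are missing, impute 01 July". It continues: "However, this should be checked not to be later than the AE stop date". The next sentence puts the start at the 1st of the stop month when a stop date is available.
- Day and month missing, AE ongoing, and 01 July later than death or end of study: 01 January.

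The section opens with a general rule that puts any date collected only as month and year on the 15th, with date of birth as its example. It does not say which rule prevails for AEs. It ends: "The same rules above (for AE date imputation) will be followed for prior / concomitant medications and medical history". First dose is not mentioned anywhere in 9.2.5.

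SAP 6.6.1, like Protocol Appendix 3.1, defines a TEAE as "any event emerging or manifesting at or after the initiation of treatment with an investigational product", or an existing event that worsens after exposure. SAP 6.6 states: "The primary analysis will be the incidence of serious TEAEs". Protocol Appendix 3.2 states: "All AEs/SAEs are collected from the time the informed consent document is signed". AEs before first dose are therefore a real category in the database.

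**The concern.** A new AE is treatment-emergent only if it starts at or after first dose, yet the imputation rule takes no account of when that was. Suppose first dose is on 15 March and a new AE after dosing is recorded only as March. The rule dates it 01 March, 14 days before dosing. The worsening part of the definition does not rescue it, because nothing existed beforehand to worsen. Neither document has a default that treats AEs of uncertain timing as TEAEs.

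With a missing day, the error goes one way: it can only remove TEAEs, which is the anti-conservative direction in a safety study. With a year-only date it can go either way. What is at stake is the content of the TEAE tables and, in principle, the serious-TEAE incidence that is the primary endpoint.

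**Working it through.** The plan gives no figure to reproduce: SAP 4.0 bases the sample size on feasibility. The check applies the rules of 9.2.5 literally to an enumeration.

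**Assumptions.** TEAE status is read from the imputed date. First-dose dates are uniform over a 365-day year. Onsets are uniform over 52 weeks plus 14 days (days 0 to 378), with no early dropout. On-treatment pairs of first-dose date and onset date: 365 × 379 = 138,335. Every percentage below applies only to AEs with the stated type of partial date.

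**Day missing.**
- A month of n days has n(n+1)/2 pairs with onset on or after first dose in that month: 7 × 496 + 4 × 465 + 406 = 5,738.
- Only a first dose on the 1st escapes the error, which accounts for 365 pairs. Placed before dosing: 5,738 − 365 = 5,373.
- 5,373/5,738 = 93.6% of first-dose-month AEs; 5,373/138,335 = 3.9% of all day-missing on-treatment AEs. No AE is lost in any later month.
- If the general 15th-of-month rule applied instead, only first doses after the 15th would be affected: 7 × 136 + 4 × 120 + 91 = 1,523. That is 26.5% of first-dose-month AEs and 1.1% overall.

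**Day and month missing, first-dose year.**
- Pairs with onset in the first-dose year: 365 × 366/2 = 66,795.
- Ongoing AE, 01 July imputed: the 183 first-dose dates after 01 July are affected, giving 183 × 184/2 = 16,836, or 25.2%. Example: first dose 14 September, imputed 01 July, 75 days early.
- 7-day AE (stop date six days after onset): the result depends on how the stop-date sentences are read. If the stop-month rule applies only when 01 July is later than the stop date, 18,519/66,795 = 27.7%. If it applies whenever a stop date exists, 3,435/66,795 = 5.1%.
- Reverse direction, onsets in the 49 days before dosing (365 × 49 = 17,885 pairs): 7,693 ongoing AEs, or 43.0%, become TEAEs.

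**Primary endpoint.** Protocol 2.2 gives earlier SAE rates of 36.6% in adults and 20.8% in children. For an assumed 15 adults and 5 children, 15 × 0.366 + 5 × 0.208 = 6.53 affected subjects.
- Every serious TEAE lacking its day: 6.53 × 0.0388 = 0.25 subjects; 0.25/20 = 1.3 percentage points.
- At an assumed 5% day-missing rate: 0.25 × 0.05 = 0.013 subjects, or 0.06 points. At 10%: 0.025 subjects, or 0.13 points.
- If all onsets fell in the first 120 days, the 3.9% becomes 5,373/(365 × 120) = 12.3%, and the 5% case becomes 6.53 × 0.123 × 0.05 = 0.04 subjects, or 0.2 points.

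**All TEAEs.** The documents give no partial-date rate. At assumed day-missing rates of 1%, 5% and 10%, 100 × rate × 0.0388 gives about 0.04, 0.19 and 0.39 AEs lost per 100 TEAEs.

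**The case against.** **The link to TEAE status is assumed.** The documents do not say that it is read from the imputed date, and a programmer might handle such cases sensibly. This stands as a limit on the consequence. The gap remains: the SAP would then leave TEAE status undefined for partial dates, and much the same added text would be needed.

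**The rules have more than one reading.** The 15th-of-month sentence literally covers a day-missing AE date, and the stop-date sentences can be read in two ways. Both points stand, so both sets of figures are shown. The AE-specific rule presumably prevails over the general one. No reading removes the error.

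**Partial dates should be rare.** AEs are reviewed at every two-weekly infusion visit (Protocol 1.2), start and stop dates are required for each change in severity (Appendix 3.3), and omissions are queried (Appendix 1.4). SAEs are reported within 24 hours of awareness (Appendix 3.4), and a hospital admission supplies its own onset date (Appendix 3.6). This stands and is why the point is minor.

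**A reader might infer that the primary result is at risk**, since one lost subject in 20 moves the incidence by 1/20 = 5 points. That requires a subject whose only serious TEAE began in the first-dose month and lacks its day, or has a year-only date that is misplaced. The expected effect is far smaller. The 6.53 subjects are probably too many, because the earlier SAE rates come from median exposures of 1.3 and 1.8 years against about one year here. A subject with a second serious TEAE would still be counted. SAP 3.1 tests no hypothesis, so no decision rule depends on the count.

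**Conclusion.** Wrong as written; minor. The rule misplaces new day-missing AEs in the first-dose month whenever dosing was not on the 1st, provided that TEAE status follows the imputed date. The 93.6% describes that narrow group and must not be read as a share of all AEs. Year-only dates in the first-dose year add a second, rarer route to error. It is not uniformly anti-conservative, so the documents do not support a claim that 9.2.5 as a whole biases TEAE counts downward. The practical effect is mainly on non-serious TEAE counts. For the primary endpoint it is very small at every partial-date rate considered, although those rates are assumptions.

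**What to change.** For AE start dates only, add to SAP 9.2.5:

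> If the known parts of a partial AE start date equal those of the first dose, and the AE stop date (or its latest possible date, if partial) is not before first dose, impute the later of the date given by the current rule and the first-dose date. An AE whose start date is partial or missing counts as a TEAE unless its known parts or its stop date show that it began or ended before first dose. The worsening part of the TEAE definition is unchanged.

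Also:

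- State that the AE-specific rule overrides the 15th-of-month rule, and make the stop-month sentence unambiguous.
- Leave 01 July unchanged in years other than the first-dose year, where no TEAE error arises.
- Write the medication and medical-history rules separately, so that they do not inherit this change.
- Take infusion-related reaction status from the investigator's record (Protocol Appendix 3.1). Of the 5,738 first-dose-month pairs, 5,738 − 365 − 353 = 5,020 (87%) start more than one day after dosing, so imputing the first-dose date could falsely meet the 24-hour window.
- Report the number of TEAEs and serious TEAEs with an imputed start date.

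In the enumeration this loses no on-treatment AE. The cost is one paragraph of text, a few lines of programming, and some pre-dose AEs counted as TEAEs. For an ongoing AE these are 5,373/17,885 = 30.0% if the day is missing (now 0%) and 16,660/17,885 = 93.2% if only the year is known (now 43.0%). For a 7-day AE with a complete stop date they are 10.8% and 12.1%. This is the conservative direction, and the reported count makes it visible.

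Protocol 9.1 requires the SAP to be final before database lock, but the documents do not give the lock status. If the database is already locked, report the reclassification as a sensitivity table.

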9.2.6 Data recorded as character values

Quantitative measurement results reported as "< X" or "<=X", i.e., below the lower limit of normal range (LLN), or "> X" or ">=X", i.e., above the upper limit of normal range (ULN), will be converted to X for the purpose of quantitative summaries, but will be presented as recorded, i.e., as "< X" or "> X" in the listings.

9.3 Analysis Software

All statistical analyses will be performed using SAS[®] (SAS Institute, Cary, NC 27513) version 9.4 or higher.

Fornon-commercialuse only
